| 11.3 | Interim Analysis | 15 |
|--------|---|----|
| 11.4 | Subgroup analysis | 15 |
| 11.5 | Statistical analyses to handle missing data | 15 |
| 11.6 | Multiple testing | 16 |
| 12 Ana | alysis of Safety Endpoints | 16 |
| 12.1 | Adverse events | 16 |
| 12.2 | Serious adverse events | 17 |
| 12.3 | Analysis for AEs and SAEs | 17 |
| 13 Der | rived Variable Definitions, Coding, and QC Plan | 18 |
| 13.1 | Derived Variable Definitions and Coding | 18 |
| 13.2 | QC Plan | 19 |
| 13.3 | Code for Primary and Secondary Analyses | 19 |
| 14 She | ell Tables | 20 |
| 15 Bib | liography | 23 |
| | | |
| | | |
| | | |
| | | |

1 SAP Signatures

I give my approval for the attached SAP for the Treatment of Meniscal Problems in Osteoarthritis: The TeMPO Trial dated March 18, 2024

Statistician (Author)

Name:

[name]

Signature:

Date:

March 18 2024

Principal Investigator

Name:

[name]

Signature:

Date:

ranch 20, 2024

2 Trial Registration

The TeMPO Trial was first registered at clinicaltrials.gov with registration No. NCT03059004. on February 14, 2017.

3 Protocol

A manuscript detailing the TeMPO rationale and design features was published as follows1:

4 Summary of Changes to the Protocol or SAP

January 2024:

The COVID-19 pandemic began in the middle of TeMPO enrollment. We have updated the SAP to include a covariate in the multivariable models indicating enrollment date prior to or after the start of the pandemic (enrollment date (prior to or after March 15, 2020)) and to include a sensitivity analysis excluding participants enrolled between January and March 2020.

We added a secondary analytic approach of the primary outcome (KOOS Pain) of baseline-adjusted ANCOVA.

Rules for missing data in computing instruments (KOOS, EQ-5D) were clarified in section 13.4.

March 2024:

A sensitivity analysis excluding participants with protocol violations that affect study eligibility or data integrity was added (section 9.4).

5 Abbreviations and Definitions

| ADL | Activities of Daily Living |
|------|--|
| AE | Adverse Event |
| APM | Arthroscopic Partial Meniscectomy |
| KLG | Kellgren-Lawrence Grade |
| KOOS | Knee Injury and Osteoarthritis Outcome Score |
| OA | Osteoarthritis |
| PT | Physical Therapy |
| RCT | Randomized Controlled Trial |

| SAE | Serious Adverse Event | |
|-----|---------------------------|--|
| SAP | Statistical Analysis Plan | |
| TKR | Total Knee Replacement | |

6 Introduction

6.1 Background and Rationale

Symptomatic knee osteoarthritis (OA) is a disabling problem affecting over 15 million adults in the US², many of whom also have MRI-based evidence of meniscal tear.³ More specifically, over 30% of persons ≥40 years old have evidence of meniscal tear on MRI³,including 80% of those with symptomatic knee osteoarthritis (OA).⁴ Relatively few tears seen on MRI cause symptoms, but those that are symptomatic are often quite disabling.³.⁴ Clinicians typically rely upon a history of mechanical symptoms to identify patients whose meniscal tears appear to be symptomatic, although the diagnostic value of mechanical symptoms is modest.⁵ In this trial we will only focus on symptomatic meniscal tear in persons with imaging evidence of OA. We refer to this phenotype as "symptomatic meniscal tear and OA" — with "OA" including both radiographic and pre-radiographic MRI evidence of cartilage damage. We focus on these patients rather than those with traumatic tear and no OA because there is more uncertainty about appropriate treatment in patients with OA.

The efficacy of therapist-directed exercise for symptomatic meniscal tear in the setting of OA has not been evaluated with placebo-controlled studies. In fact, a recent literature synthesis by the American Physical Therapy Association identified *no* studies establishing the efficacy of conservative management of symptomatic meniscal tear.⁶ This is a key research gap: there is currently no evidence as to whether any PT regimen is superior to placebo in persons with symptomatic meniscal tear and OA. This is a particularly pressing issue, as the lack of evidence supporting the superiority of surgery has more and more doctors turning to physical therapy as the first line of treatment.

In summary, symptomatic meniscal tear in the presence of OA is a prevalent, disabling, costly problem. Therapist-directed exercise and manual therapy have been associated with substantial pain relief in OA⁷⁻¹² but have not been studied in symptomatic meniscal tear with OA. Further, we do not know whether the pain relief observed in OA trials is due to the physiologic effects of strengthening and manual therapy, placebo effect due to attention from a therapist; the effect of enrolling in a trial, or natural history. The premise of the TeMPO Trial builds upon rich data in the chronic disease literature that suggests each of these factors may contribute to treatment efficacy. The different aspects of treatment must be distinguished to develop objective clinical and policy recommendations; these factors can only be disentangled with a carefully designed RCT, involving placebo elements.

6.2 Scope of Analysis

These analyses will assess the efficacy of home-based exercise compared to physical therapy among patients who have meniscal tear and osteoarthritis.

7 Study Objectives

7.1 Primary Objective

To conduct a multicenter, parallel, four-arm randomized controlled trial that will establish the efficacy of various components of the typical PT regimen for subjects 45-85 with symptomatic meniscal tear. The four arms will include:

- Arm 1: Prescription of an information-based (exercise pamphlet, DVD) home exercise program
- Arm 2: An information-based home exercise program (exercise pamphlet, DVD) with adherence optimization
- Arm 3: Same as Arm 2 plus a clinic-based, therapist-directed sham intervention, with no known physiologic effect
- Arm 4: Same as Arm 2 plus "true PT": clinic-based, therapist-directed exercise and manual therapy

The three primary hypotheses are:

Therapist-directed exercise and manual therapy plus optimized home exercise (Group 4) will lead to greater improvement in KOOS pain at three months than simple prescription of a home exercise program (Group 1).

Therapist-directed exercise and manual therapy plus optimized home exercise (Group 4) will lead to greater improvement in KOOS pain at three months than optimized home exercise and no interaction with a therapist (Group 2).

Optimized home exercises (Group 2) will have a greater effect on KOOS pain at three months than simple prescription of exercises without adherence optimization (Group 1).

7.2 Secondary Objectives

Secondary objectives include testing the additional hypotheses that:

In-clinic placebo PT plus optimized home exercise (Group 3) will lead to greater improvement in KOOS pain at three months than optimized home exercise and no interaction with a therapist (Group 2).

Therapist-directed exercise and manual therapy plus optimized home exercise (Group 4) will lead to greater improvement in KOOS pain at three months than in-clinic placebo PT plus optimized home exercise (Group 3).

Secondary objectives also include assessing secondary outcome measures and longer term durability of the treatment effect.

8 Study Methods

8.1 Trial Design

The TeMPO Trial is a four-arm single-blind multi-center randomized controlled clinical trial. The treatment allocation ratio is 1:1:1:1.

| Table 1. Study Arms | | | | | | | | | | | |
|---------------------|--|---------------------------|-------------------------------------|--|--|--|--|--|--|--|--|
| Arm | Protocolized Home Exercise Program | Adherence Optimization | Placebo Therapy (14 sessions) | Supervised Exercise & Manual Therapy (14 sessions) | | | | | | | |
| Arm 1 | ✓ | | | | | | | | | | |
| Arm 2 | ✓ | √ | | | | | | | | | |

| Arm 3 | √ | ✓ | ✓ | |
|-------|----------|----------|---|---|
| Arm 4 | ✓ | ✓ | | ✓ |

8.2 Randomization

A randomization schedule was created to randomize subjects to 1 of 4 treatment arms in a 1:1:1:1 fashion using permutated blocks with randomly varying block sizes 4 and 8. Randomization is stratified by study site and by baseline Kellgren-Lawrence (KL) grade (0-2 vs. 3). The randomization schedule is uploaded to the TeMPO REDCap data management system and research coordinators will obtain arm assignments through this system.

8.3 Blinding

This trial is a single-blind study. The Analysis Core, including the Statistician and Principal Investigator, will be blinded to the subject's treatment assignment to avoid bias. Research coordinators communicating with the TeMPO subjects about outcomes assessment and performing follow-up assessments (i.e., performance tests, strength testing) are blinded to the subject's arm assignment. All other individuals, including the study subject, are not blinded. All subjects will be told during the informed consent procedure that this study has a placebo element. However, we will not specify what the placebo element is. Subjects will also be informed that all groups will receive at least some active intervention. The analysis will be done with group status masked; identification of each arm will not be revealed until the analyses are completed.

8.4 Study Assessments

| | | | | Tel | MPO Schedule o | | | | | | | | | | | |
|------------------------------|-------------------|------------|---------------------|---------|-------------------|------|------------|--------|------------|-------------|-------------|-------------------|----------|------------|-------------|-------------|
| | Study Timepoint | | | | | | | | | | | | | | | |
| Study Form | Pre- Sureening | Someoning | Enrollment Visit | lmaging | Randomizatio n | | 4 weeks | | 8 weeks | 10 weeks | 12 weeks | Hweeks (Islaw- | | 5 month | 12 mondi | As Neede |
| Pre-screening | X | | | | | | | | | | | | | | | |
| Screening | | Χø | | | | | | | | | | | | | L | |
| Physician Diagnosis | | Х* | | | | | | | | | | | | | | |
| Baseline Visit Tracking Form | | Х | X | | | | | | | | | | | | | T |
| MSK Exam | | | Х* | | | | | | | | | X | | | | T |
| Patient Questionnaire | | χ* | Х* | | | | | | | | | X* | | Х* | χ* | 909to |
| Image Assessment | | | | X | | | | | | | | | | | | T |
| Randomization Form | | | | | X | 11.5 | 200 | 15.50 | | S 2511 | | 3.111111 | 100 | | | |
| Post-Randomization Tracking | | | | | X | X | | Τ | Γ | I | | | T | | T | T |
| Health Pamphlet Mailing | | | | | X* | Х* | Х* | Х* | Х* | Х* | Х* | | | | | T |
| Home exercise log | | | | | | X | X | X | X | X | X | | | | | T |
| PT form | | 2 11111111 | | | | 100 | | 11/2/2 | | 100 | | | 133. 133 | | | X |
| 6 week call | | | | | 1 | | | X | | | | | T | Ī | | T |
| PT Summary Form | | | | | | | | | | | | | Х | | | |
| Medical Record Review | | | | | | | X | | X | | X | | | Х | X | é |
| Reumuneration Form | | | | | X | | X | | X | | X | | X | X | Х | § . |
| AEForm | | | | | | | | | | | | | | | | X |
| Protocol Deviation Form | | | | | | | | | | | | | | T | | X |
| Injection Form | | | | | | | | | | | | | | | | X |
| Discontinuation Form | | | 1 | | | | | | | | | | | | I | Х |

Key Filled out by Research Assistant Filled out by Physician Filled out by Subject Filled out by Radiologist Filled out by Therapist X* = potentially hard copy

X = performed by blinded staff member
X = done by BWH only

kalic study timepoint = seen by blinded assessors

10

8.5 Sample Size

We power the trial to detect a modest effect of 0.33 SD, reasoning that patients and clinicians will adopt treatments with modest effects if the intensity of treatment and risk of harm is low. As the KOOS Pain scale had a baseline SD of 16 points in MeTeOR, an effect size of 0.33 SD equates to 5.3 points, less than the estimated minimally clinically important difference for the KOOS Pain scale of 8-10 points^{9,13}. We envision that the difference between Arm 1 (least intensive) and Arm 4 (most intensive) will be 10-12 points and that the comparisons of Arms 1 vs. 2 (effect of adherence optimization), 2 vs. 3 (additional provider interaction), and 3 vs. 4 (additional therapist-directed exercise and manual therapy) will represent components of this overall difference. Thus, our plan to power for a difference of 5.3 points in pairwise comparisons should provide adequate power for all contrasts. We assume 80% power and Type I error of 0.0167 to reflect three comparisons of strategies that would be used in practice (Arms 4 vs. 1; Arms 4 vs. 2; Arms 2 vs. 1). Given these considerations and balanced allocation across arms, each Arm would need 194 subjects. Allowing for 10% dropout at one year we will require 194 x 1.1 = 214 subjects per Arm, 856 in total.

9 Analytic Considerations

9.1 Hypotheses

This study will address the following hypotheses, summarized in Table 2:

| Table 2. Study Hypotheses | | | | | | | | | | | |
|---------------------------|-----------------------|--|-----------------------|------------------------------------|--|--|--|--|--|--|--|
| Arm | Arm 1 (home exercise) | Arm 2 (home exercise w/adherence optimization) | Arm 3 (placebo PT) | Arm 4 (therapist- delivered PT) | | | | | | | |
| Arm 1 | | | | | | | | | | | |
| Arm 2 | H3 | | | | | | | | | | |
| Arm 3 | | H4 | | | | | | | | | |
| Arm 4 | H1 | H2 | H5 | | | | | | | | |

Primary Hypotheses:

Hypothesis 1: Arm 4 (protocolized home program, adherence optimization, in-clinic physical therapist-delivered exercise and manual therapy) is more efficacious than Arm 1 (protocolized home program alone). This analysis contrasts the putatively most potent intervention against the least potent.

Hypothesis 2: Arm 4 (protocolized home program, adherence optimization, in-clinic physical therapist-delivered exercise and manual therapy) is more efficacious than Arm 2 (protocolized home program with adherence optimization). This contrast isolates the effect of the in-clinic physical therapist-delivered intervention of exercise and manual therapy.

Hypothesis 3: Arm 2 (protocolized home program with adherence optimization) is more efficacious than Arm 1 (protocolized home program without adherence optimization). This contrast isolates the effect of the adherence optimization program.

Secondary Hypotheses:

Hypothesis 4: Arm 3 (protocolized home program, adherence optimization, in-clinic placebo PT) is more efficacious than Arm 2 (protocolized home program with adherence optimization). This contrast isolates the effect of attending an in-clinic program that provides face to face contact and support by clinicians with essentially no physiological effect directed at musculoskeletal impairments.

Hypothesis 5: Arm 4 (protocolized home program, adherence optimization, in-clinic physical therapist-delivered exercise and manual therapy) is more efficacious than Arm 3 (protocolized home program with adherence optimization and placebo PT). This contrast compares the effects of "active" PT and placebo PT, both given along with protocolized home exercises.

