11.1 Primary Analysis

In the primary analysis we will test the 3 hypotheses outlined in section 7.1. As placebo is not used in practice, we do not consider tests involving Arm 3 as one of our multiple comparisons. For the primary analysis the alpha level is adjusted to 0.0167 to account for 3 comparisons. We will adjust for randomization arm, the randomization stratification factors of study site and baseline KL grade (0-2 vs. 3) as well as baseline KOOS pain and enrollment date (prior to or after March 15, 2020).

We will use linear regression as our main analytic approach, as our primary outcome of change in KOOS pain is continuous. The primary analysis will be complete case. Data will be summarized by treatment group with the number, mean, and standard deviation. 98.3% Cis will be used to summarize the three between-group comparisons of interest.

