11.2 Secondary Analyses

11.2.1 Secondary Hypotheses

In a similar fashion to the primary analysis, we will test the two secondary hypotheses outlined in section 7.2 for the outcome of 3 month KOOS pain.

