11.5 Statistical analyses to handle missing data

We anticipate ~5% dropout at 3 months and ~10% at 12 months based on dropout rates from the Meniscal Tear in Osteoarthritis Research (MeTeOR) RCT⁹. We will address dropout and other forms of missing data first by reporting the number of subjects dropping out in each arm and the reasons for dropout. We will determine whether the frequency of these dropouts differs across study arms. We will examine the distribution of baseline covariates and baseline KOOS pain in subjects dropping out compared to those completing the study. Our primary assumptions

are that data will be missing at random (MAR), and that dropout will not depend on unobserved outcomes.

We will perform sensitivity analysis for missing data for our primary outcome of KOOS pain and our secondary outcomes of KOOS ADL, EQ-5D, strength measures, objective function measures, and treatment failure for our three primary hypotheses. We will use linear mixed effects models to analyze the continuous outcomes of KOOS pain, KOOS ADL, and EQ-5D. Models will be adjusted for timepoint, randomization arm, the randomization stratification factors of study site and baseline KL grade (0-2 vs. 3) as well as the baseline value of the outcome and enrollment date (prior to or after March 15, 2020). A timepoint by treatment arm interaction term will test whether change from baseline to 3 months differs between treatment arms. Linear mixed-effects models can handle imbalanced data and are appropriate for data that are missing at random.

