11.6 Multiple testing

In the primary analysis we will test the 3 hypotheses outlined in section 7.1. As placebo is not used in practice, we do not consider tests involving Arm 3 as one of our multiple comparisons. For the primary analysis the alpha level is adjusted to 0.0167 to account for 3 comparisons. Secondary hypotheses and outcomes will not be adjusted for multiple testing.

12 Analysis of Safety Endpoints

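### SAP section 8.5 claims adequate power for all contrasts, but the envisioned 10-12 points cannot give all three adjacent-arm contrasts 80% power on the plan's SD and sample size

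*SAP*

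**What the plan says.** SAP section 8.5 sizes the trial for one pairwise contrast: "an effect size of 0.33 SD equates to 5.3 points", with SD 16, 80% power and a type I error of 0.0167, giving 194 per arm and 214 after allowance for dropout.

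The same section gives the expected size of the largest contrast: "We envision that the difference between Arm 1 (least intensive) and Arm 4 (most intensive) will be 10-12 points". It says that the comparisons of Arms 1 vs 2, 2 vs 3 and 3 vs 4 "will represent components of this overall difference". From this it concludes: "Thus, our plan to power for a difference of 5.3 points in pairwise comparisons should provide adequate power for all contrasts".

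Under section 9.1, the three adjacent comparisons are H3 (primary, tested at 0.0167), H4 and H5 (both secondary). For the secondary ones, section 11.2.1 says "In a similar fashion to the primary analysis, we will test the two secondary hypotheses outlined in section 7.2", and section 11.6 says "Secondary hypotheses and outcomes will not be adjusted for multiple testing". No alpha is printed for H4 and H5, and no size is given for any single component.

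**The concern.** The three adjacent differences add up exactly to the Arm 4 vs Arm 1 difference. If the total is 10-12 points, they cannot all be 5.3 points, because that would need 15.9. The power statement therefore conflicts with the effect sizes given just before it.

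H4 and H5 separate the effect of contact with a provider from the effect of active therapy, which section 6.1 gives as the reason for including placebo elements. With this sentence in the plan, a non-significant H3, H4 or H5 could be read as coming from an adequately powered comparison when at least one of them cannot have that power on the plan's own figures.

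**Working it through.** **Inputs.** From section 8.5: SD 16, difference 0.33 × 16 = 5.28 (stated as 5.3), power 80%, alpha 0.0167, 194 evaluable per arm, 214 randomised per arm, total difference 10-12. From section 11.5: about 5% dropout at 3 months, so 214 × 0.95 ≈ 203 evaluable at the primary endpoint. Assumed, because the SAP does not print it: two-sided 0.05 for H4 and H5.

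**Method.** Two-sample noncentral t with df = 2n − 2 and noncentrality δ / (SD × √(2/n)). At n = 194 the standard error is 16 × √(2/194) = 1.625.

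**Step 1: the plan's own figure.** n = 194, δ = 5.28 and two-sided alpha 0.0167 give power 0.801. The 194 is reproduced. A one-sided calculation (normal approximation) gives 161-162 and does not reproduce it.

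**Step 2: the sum.** (Arm 4 − Arm 1) = (Arm 2 − Arm 1) + (Arm 3 − Arm 2) + (Arm 4 − Arm 3), that is, H1 = H3 + H4 + H5. The smallest part is at most one third of the total: 10/3 = 3.33 or 12/3 = 4.0 points.

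**Step 3: the total needed for 80% power on each part** (SD 16, no gain from adjustment).

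| n per arm | Detectable at 0.0167 | Detectable at 0.05 | H3 at 0.0167, H4 and H5 at 0.05 |
|---|---|---|---|
| 194 | 5.27 | 4.56 | 5.275 + 2 × 4.563 = 14.4 |
| 203 | 5.16 | 4.46 | 14.1 |
| 214 (no dropout) | 5.02 | 4.34 | 13.7 |

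Every total exceeds 12. With all three at 0.0167 and n = 194 it is 3 × 5.275 = 15.8.

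**Step 4: power for the smallest part** (n = 194). These are ceilings over every possible split.

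| Total | Smallest part, at most | If it is H3 (0.0167) | If it is H4 or H5 (0.05) |
|---|---|---|---|
| 10 | 3.33 | 36% | 53% |
| 12 | 4.0 | 52% | 69% |

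If H3 does reach 5.3, then H4 + H5 is 4.7 (total 10) to 6.7 (total 12). The smaller of the two is at most 2.35 to 3.35 points, with at most 30% to 54% power at 0.05.

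**Step 5: the primary family.** H1 = H2 + H3. H1 at 10 points or more has over 99% power. H2 and H3 can both reach 5.3 if the total is at least 10.6 and is split nearly evenly. At 5 + 5, each has 75% power (77% with 203 per arm); at 6 + 6, each has 90%.

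**Step 6: baseline adjustment.** Assume a 3-month SD of 16 and a baseline to 3-month correlation r, so that the residual SD is 16 × √(1 − r²). With n = 194:

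| r | Residual SD | Total needed for 80% on all three |
|---|---|---|
| 0.3 | 15.3 | 13.7 |
| 0.5 | 13.9 | 12.5 |
| 0.7 | 11.4 | 10.3 |

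The total needed falls to 12 at r = 0.55 and to 10 at r = 0.72 (0.52 and 0.70 with 203 per arm). At r = 0.5 with an equal split, power is 49-67% for H3 and 66-81% for H4 and H5.

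**The case against.** Four arguments can be made for the plan.

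- **Baseline adjustment.** Section 11.1 adjusts the primary model for the stratification factors "as well as baseline KOOS pain and enrollment date", so the working SD may be below 16. This is the strongest point: at a total of 12, whether the claim fails depends on a correlation that the SAP does not give. But section 8.5 takes no credit for adjustment, the correlation would have to reach 0.55 to 0.72, the points would also have to split in the most favourable way, and a 3-month SD above 16 would work the other way.
- **More evaluable participants at 3 months.** Section 11.5 says "We anticipate ~5% dropout at 3 months and ~10% at 12 months", which leaves about 203 per arm. This stands, but it moves the total needed only from 14.4 to 14.1. The ceilings in step 4 become 38-55% and 55-71%.
- **Only the primary contrasts are meant.** The sentence after the claim ties 80% power to Arms 4 vs 1, 4 vs 2 and 2 vs 1, and section 11.1 leaves Arm 3 out of the multiplicity count. But the claim is drawn directly from a sentence naming 2 vs 3 and 3 vs 4. If only H1 to H3 are meant, the text must say so.
- **Secondary hypotheses need no guaranteed power, and nothing in the analysis depends on it.** Both are true, and nothing in the SAP commits the authors to misreading a null result. The fault is that the plan asserts a power it does not have.

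The 0.05 for H4 and H5 is an assumption in the plan's favour; 0.0167 throughout makes the shortfall larger.

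**Conclusion.** The concern holds. No split of 10-12 points gives H3, H4 and H5 each 80% power with 194 per arm and SD 16: about 14.4 points are needed. At least one of the three has power no higher than 36-52% (if H3) or 53-69% (if H4 or H5).

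This rests on two-sided tests, 0.05 for H4 and H5, and no gain from baseline adjustment. Only a baseline correlation of roughly 0.55 or more, together with the most favourable split, would change it.

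The sample size calculation is not wrong, and the primary family as a whole is not shown to be underpowered. The error is the step from one 5.3-point contrast to all contrasts. It should be corrected because it bears on how null component results are read.

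**What to change.** Replace the sentence in section 8.5 with wording such as:

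> With 194 evaluable per arm, power is 80% at 0.0167 for any pairwise difference of 5.3 points (SD 16, no gain from baseline adjustment). The envisioned 10-12 points cannot make all three adjacent components this large. As an illustration, with an equal split (3.3-4.0 points each) unadjusted power is about 36-52% for H3 at 0.0167 and about 53-69% for H4 and H5 at two-sided 0.05. Baseline adjustment raises this by an amount that depends on the baseline to 3-month correlation (for example 49-67% and 66-81% at an assumed 0.5). Non-significant component contrasts will be interpreted from their confidence intervals, not as absence of effect.

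The equal split, the 0.05 and the correlation are illustrative and should stay labelled as such, or be replaced by the authors' own values. The minimum change is to limit the claim to differences of at least 5.3 points and drop the reference to all contrasts.

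The cost is SAP wording only, with a less favourable stated power for the component contrasts. Sample size, alpha and analysis do not change.

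### The 10% dropout allowance in SAP section 8.5 multiplies by 1.1 instead of dividing by 0.9, so 214 per arm leaves 192–193 rather than 194 at that loss; the effect is small and does not threaten the 3-month primary comparison

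*SAP*

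**What the plan says.** SAP section 8.5 builds the sample size from a standardised effect ("We power the trial to detect a modest effect of 0.33 SD"), with the conversion to points given as "baseline SD of 16 points in MeTeOR, an effect size of 0.33 SD equates to 5.3 points". The error rates are stated as "We assume 80% power and Type I error of 0.0167 to reflect three comparisons", and section 8.1 fixes equal allocation ("The treatment allocation ratio is 1:1:1:1"). From these, section 8.5 concludes that "each Arm would need 194 subjects". The enrolment figure follows in one step, as an allowance for 10% loss by one year: "194 x 1.1 = 214 subjects per Arm, 856 in total".

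Section 11.5 gives dropout by time point: "We anticipate ~5% dropout at 3 months and ~10% at 12 months". Section 9.2 places the primary outcome, change in KOOS Pain, at 3 months, and section 11.1 makes the primary analysis complete case.

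**The concern.** Dropout is a fraction of those enrolled, so the number to enrol is the evaluable number divided by the retained fraction. Section 8.5 instead adds 10% of the evaluable number. That always falls a little short, and here the printed 214 does not keep the 194 that the same paragraph requires. The formula is printed in full, so the slip does not depend on how the text is read.

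What is at stake is whether the sample-size justification follows from its own inputs, since readers commonly recalculate this paragraph. Section 8.5 also uses only the 12-month dropout rate, so it does not show how many subjects the primary 3-month complete-case comparison is expected to keep.

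**Working it through.** **Inputs.** Effect 0.33 SD, SD 16 points, difference 5.3 points, power 80%, alpha 0.0167, 194 evaluable per arm and 10% dropout at one year (all section 8.5); four equal arms (section 8.1); about 5% dropout at 3 months and about 10% at 12 months (section 11.5). The sidedness of alpha and the test behind the calculation are not stated.

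**Step 1: reproduce 194.** For a two-sample t-test with d = 0.33, two-sided alpha 0.0167 and 80% power, n = 193.6, rounded up to 194 per arm. This matches. The normal approximation, n = 2(z₁₋α/₂ + z₁₋β)² / d² = 2(2.393 + 0.842)² / 0.33², gives 192.2, so 193. A one-sided alpha gives 162, which does not match. Two-sided testing is therefore assumed below.

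**Step 2: reproduce 214 and 856.** 194 × 1.1 = 213.4, rounded up to 214; 4 × 214 = 856. Both match.

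**Step 3: check what 214 retains.**
- At 10% loss: 214 × 0.90 = 192.6, below 194.
- Largest loss that still keeps 194: 1 − 194/214 = 0.0935, so just over 9.3%.
- Inflation that does what the sentence intends: 194 / 0.90 = 215.6, so 216 per arm and 4 × 216 = 864 in total.
- Difference: 2 per arm, 8 in total, 8/856 = 0.9%.
- At 5% loss: 214 × 0.95 = 203.3, above 194.

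**Step 4: power at the numbers retained** (two-sided alpha 0.0167, t-test unless noted).

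| Evaluable per arm | Situation | d = 0.33 | d = 5.3/16 = 0.33125 | d = 0.33, normal approximation |
|---|---|---|---|---|
| 192 | 10% loss, rounded down | 79.6% | 80.0% | 80.0% |
| 193 | 10% loss, rounded up | 79.9% | 80.2% | 80.2% |
| 194 | stated requirement | 80.1% | 80.4% | 80.4% |
| 203 | 5% loss (3 months) | 82.1% | 82.4% | 82.4% |

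The shortfall at 10% loss costs less than half a percentage point of power. Which side of 80% it falls on depends on the third decimal of d and on the method.

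**The case against.** The strongest reply is that no powered analysis is affected, and this stands. The calculation serves the three primary contrasts, all at 3 months, where the SAP expects about 5% dropout. For that rate, 194 / 0.95 = 204.2, so 205 per arm would be enough, and 214 exceeds it. The shortfall appears only at 10% loss, which the SAP expects at 12 months. No contrast is powered there: durability is descriptive (section 11.2.2.2) and longitudinal KOOS uses mixed models over all time points (section 11.2.2.3). The primary model also adjusts for baseline KOOS Pain (section 11.1), which the calculation does not credit.

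A reader might infer that the primary comparison has less power than stated. The documents do not support this: at the expected 3-month dropout, power is about 82%, above the 80% planned. A reader might also infer that a 12-month rate applied to a 3-month outcome is an error. It is not. Section 8.5 labels the rate as a one-year figure, it agrees with section 11.5, and it is conservative for the primary outcome.

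The reply does not rescue the sentence itself. As printed, it claims to allow for 10% dropout, and 214 per arm does not keep 194 at that rate.

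**Conclusion.** A certain but minor arithmetic slip. Section 8.5 inflates with the wrong formula, so 214 per arm leaves about 192–193 at the stated 10% loss instead of 194, and its own inputs lead to 216 per arm (864). The firm point is the inconsistency between inputs and result. The loss of power is too small to rest anything on: at 10% loss, power is essentially 80%.

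The power figures assume two-sided testing at 0.0167 and an unadjusted two-sample comparison with an effect of 0.33 SD; the retention figures use the SAP's own dropout rates and need no further assumption.

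**What to change.** Keep 856 and restate the last sentence of section 8.5. Remove the multiplication by 1.1 and say what 214 per arm is expected to leave: about 203 at 3 months (5% dropout, about 82% power for each primary contrast) and about 192–193 at 12 months (10% dropout, about 80% power on the same assumptions). State in the same place that alpha is two-sided, if that is what was intended. This also brings section 8.5 into line with the dropout rates in section 11.5.

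The cost is one sentence, with no change to enrolment, design or analysis. Raising the target to 864 would mean 8 more participants for a negligible gain, and the primary comparison does not need them.
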